7.1.2 Categorical Secondary Endpoints

The null hypothesis for secondary endpoints 7 and 8 is that there is no difference in the endpoint proportions for the treatment and control arms (indicating equality). Rejection of the null hypothesis indicates the observed data supports the alternative hypothesis that a difference in the endpoint proportions exits between the treatment and control arms (indicating inequality). The hypotheses associated with these secondary endpoints are:

$$H_0$$
: $p_t - p_c = 0$
 H_1 : $p_t - p_c \neq 0$

where p_t and p_c are the endpoint proportions for the treatment and control arms, respectively.

8 Analysis of Exploratory Endpoints

The exploratory endpoints are evaluated at the week 12 follow-up visit and compare the treatment and control arms. Analysis of the exploratory endpoints evaluates the following:

- 1. Time from enrollment to hospitalization for a COPD or other respiratory condition-related inpatient hospitalization ≥ 24 hours
- 2. Number of days in hospital for COPD or other respiratory condition-related inpatient hospitalization ≥ 24 hours
- 3. All-cause unplanned hospitalizations
- 4. Change in average daily activity duration and intensity
- 5. Change in average energy expenditure/day

Exploratory endpoint 1 will be analyzed with a Cox proportional hazard model, using time to hospitalization as the response and treatment arm, center, age, and baseline 6MWT as predictors. The model will be summarized with regression coefficient estimates and standard deviations.

For exploratory endpoint 4, the baseline and week 12 follow-up visit values are the average value during the first and twelfth weeks of the study, respectively. For accuracy, only wake- and wear-filtered ActiGraph data will be used in the analysis. Exploratory endpoint 4 will be summarized in the following ways:

- Change in average duration per day at each intensity from baseline to the week 12 follow-up visit
- Average duration per day at each intensity over 12 weeks
- Change in percentage of time spent engaging in Sedentary to Very Low Physical Activity (SVLPA) from baseline to the week 12 follow-up visit

 Proportion of subjects engaging in Moderate to Vigorous Physical Activity (MVPA) at the week 12 follow-up visit who did not at baseline

For exploratory endpoint 5, the baseline and week 12 follow-up visit values are the average value during the first and twelfth weeks of the study, respectively. For accuracy, only wear-filtered ActiGraph data will be used in the analysis.

Exploratory endpoints 2-5 will only be summarized with descriptive statistics and will not have formal hypothesis testing performed.

9 Analysis of Adverse Events

All adverse events occurring during the study will be summarized by type, seriousness, Investigator-reported relatedness (to the study procedure and the LTOT, POC, and ActiGraph devices), severity, and outcome with the number of events experienced and the number and percentage of subjects experiencing the event. Adverse events will also be summarized in a listing. No formal hypothesis testing will be performed.

9.1 Seriousness

An adverse event is serious if it:

- Leads to death
- Leads to serious deterioration in the health of a patient that:
 - o results in a life-threatening illness or injury,
 - o results in permanent impairment of a body structure or body function.
 - o requires inpatient hospitalization ≥ 24 hours or prolongation of existing hospitalization, or
 - o results in medical or surgical intervention to prevent permanent impairment to a body structure or a body function.

9.2 Severity

Adverse events will be categorized by the Investigator as mild, moderate, or severe, depending on the event's impact on the subject's daily activity level:

- Mild: Usually transient, requiring no special treatment; does not interfere with the subject's daily activities.
- Moderate: Low-level inconvenience or concern to the subject; may interfere with daily activities, usually resolved by simple therapeutic non-interventional methods.
- Severe: Interruption in subject's daily activity requiring systemic drug therapy or other treatment.

9.3 Relatedness

Adverse events will be judged by the Investigator as to their relatedness to the study procedure and the LTOT, POC, and ActiGraph devices using the following classifications:

- Unrelated: The event is due to the underlying disease state or concomitant medication or therapy not related to the study-specific devices or procedures.
- Probably Not Related: The event had no significant temporal relationship to the study-specific devices or procedures and/or a more likely alternative etiology exists.

- Possibly Related: The event had a strong temporal relationship to the study-specific devices or
 procedures and alternative etiology is equally or less likely compared to the potential relationship
 to the study-specific devices or procedures.
- Probably Related: The event had a strong temporal relationship to the study-specific devices or procedures and another etiology is unlikely.
- Unknown: Relationship of the event to the study-specific devices or procedures and alternative etiology is unknown.

10 Measurements, Scales, and Subject-Reported Outcomes

10.1 ActiGraph Measurements

The ActiGraph GT9X Link wearable device continuously collects data including calories expended; duration of physical activity; X-, Y-, and Z-axis activity counts; steps taken; whether the subject is sleeping; and whether the device is being worn among many other measures. For the purposes of this study, only data recorded while the subject is wearing the device (wear-filtered) will be used. Certain measurements also only use data recorded while the subject is awake (wake-filtered) or asleep (sleep-filtered).

10.1.1 Total Energy Expenditure

The total energy expenditure (TEE) is the total number of wear-filtered kilocalories expended in a day.

10.1.2 Sleep Energy Expenditure

The sleep energy expenditure (SEE) is the total number of sleep- and wear-filtered kilocalories expended in a day.

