9.4.1 Physical Activity Level (PAL)

As it relates to the primary study endpoint, PAL will be calculated using the following ratio:

$$\frac{\text{Total Energy Expenditure (TEE) (kcal)}}{\text{Sleep Energy Expenditure (SEE) (kcal)}}$$

The TEE measurement is reported directly by ActiGraph. The baseline calculation will use the average wear-filtered TEE reported within the first week of study participation. The 12-week calculation will use the average wear-filtered TEE reported within the twelfth week of study participation.

The baseline SEE measurement will be derived from average TEE values reported only during the patient's sleep time within the first week of study participation. The 12-week SEE measurement will be

derived from average TEE values reported only during the patient's sleep time within the twelfth week of study participation.

Note: The TEE measurement will also be reported as a stand-alone measurement as a representation of average energy expenditure per day (see section 9.4.4 below).

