5.4 Adverse Events

All adverse events will be recorded and reported.

6 Analysis of Primary Effectiveness Endpoint

The primary effectiveness endpoint analysis evaluates the difference in the mean change in PAL from baseline to the week 12 follow-up visit between the treatment and control arms. For accuracy, only wear-filtered ActiGraph data will be used in the analysis. The baseline PAL uses the average TEE and average SEE values during the first week of the study and the week 12 follow-up visit PAL uses the average values from the twelfth week of the study. Only subjects with available baseline and week 12 follow-up visit PAL values will be included in this analysis.

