10.1.3 Physical Activity Level

As it relates to the primary effectiveness endpoint, physical activity level (PAL) is the ratio of TEE to SEE, both as defined above, expressed as the following fraction:

Total Energy Expenditure (TEE)
Sleep Energy Expenditure (SEE)

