11.1.2 Per Protocol

The per protocol analysis set (PP) consists of subjects in the ITT analysis set that did not experience any of the following major protocol deviations:

- Violations of inclusion/exclusion criteria for study
- Non-compliance (less than 18 hours of ActiGraph wear-time in a day) of more than two days during the first or twelfth week after enrollment

The PP analysis set will only be used, if different than the ITT analysis set, in a secondary analysis of the primary effectiveness endpoint assessing the sensitivity to the choice of analysis set.

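### The primary endpoint PAL is total worn kcal over total worn sleep kcal, with neither term divided by its time, so it moves with sleep length and uneven non-wear as well as with activity

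*SAP*

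**What the plan says.** SAP 10.1.1 defines the numerator: "The total energy expenditure (TEE) is the total number of wear-filtered kilocalories expended in a day". SAP 10.1.2 defines the denominator: "The sleep energy expenditure (SEE) is the total number of sleep- and wear-filtered kilocalories expended in a day". SAP 10.1.3 then states that "physical activity level (PAL) is the ratio of TEE to SEE, both as defined above". SAP section 6 fixes the averaging: "The baseline PAL uses the average TEE and average SEE values during the first week of the study", with the same rule for week 12. Nothing in either document divides a term by hours, rescales to 24 hours or adjusts for sleep length.

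On wear, SAP 10.1 says that "only data recorded while the subject is wearing the device (wear-filtered) will be used". The primary analysis adds no wear minimum: "Only subjects with available baseline and week 12 follow-up visit PAL values will be included in this analysis". The only threshold is a major deviation in SAP 11.1.2: "Non-compliance (less than 18 hours of ActiGraph wear-time in a day) of more than two days during the first or twelfth week after enrollment". It defines the per-protocol set, which is used only for a sensitivity analysis of the primary endpoint, and it does not separate sleeping from waking hours.

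Protocol 9.4.1 labels both terms in kcal and derives SEE from average TEE values during sleep, without saying whether the average is per day or per minute. Protocol 14.1 describes PAL as daily total over sleep expenditure. The sample size sections (Protocol 14.2, SAP 6.2) use a difference of 0.1 and an SD of 0.22, and give no source or scale for either.

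**The concern.** The two totals cover different lengths of time: all worn hours above the line, worn sleep hours below it. Their ratio mixes how intensely the patient lives while awake with how many hours the device recorded as sleep. Wear filtering drops unworn minutes but does not restore the balance when those minutes fall mainly in sleep or mainly in waking time.

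At stake is what a PAL result can be said to show. The study's purpose is to evaluate activity. If sleep or wear changed between weeks 1 and 12, a PAL difference could not be read as an activity difference without further evidence, and any such variation that the planning SD omits would cost power.

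**Working it through.** **The plan's own figure.** A two-sample t-test with difference 0.1, SD 0.22 and two-sided 5% needs 77 per arm (power 80.0%). This reproduces the stated 77.

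**Assumptions.** The documents give neither sleep hours s nor the waking/sleeping kcal rate ratio r. I take s = 8 h and r = 1.0 to 1.5, with a fully worn 24 h day unless stated.

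**Formulas.**
- Totals (SAP): PAL = [s + r(24 − s)]/s = 1 + r(24 − s)/s. Slope: −24r/s² per hour of sleep.
- Same time base: PAL = [s + r(24 − s)]/24. Slope: −(r − 1)/24 per hour.

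**No activity above sleep level (r = 1).** Totals PAL is 24/s: 3.00 at 8 h, 3.43 at 7 h, 4.00 at 6 h. The rate version stays at 1.00.

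**Sleep change that moves totals PAL by 0.1 from s = 8 (exact).** New s = 24r/(3r ± 0.1).
- Rise of 0.1: 15.5 min less sleep (r = 1.0), 10.4 min less (r = 1.5).
- Fall of 0.1: 16.6 min more (r = 1.0), 10.9 min more (r = 1.5).

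**If 0.1 is a rate-scale value.** The totals scale is 24/8 = 3 times the rate scale, so the equivalent is 0.3. The changes are 43.6 and 30.0 min less sleep for a rise, and 53.3 and 34.3 min more for a fall. Scale matters for activity too. At fixed 8 h sleep, 0.1 on totals is a rise in r of 0.1 × 8/16 = 0.05; on the rate scale it is 0.1 × 24/16 = 0.15.

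**Activity and sleep changing together (start r = 1.5, s = 8).**

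| r, s | Totals | Same time base |
|---|---|---|
| 1.5, 8.0 | 4.00 | 1.333 |
| 1.6, 8.5 | 1 + 1.6 × 15.5/8.5 = 3.92 | 33.3/24 = 1.388 |
| 1.4, 7.5 | 1 + 1.4 × 16.5/7.5 = 4.08 | 30.6/24 = 1.275 |
| 1.6, 7.5 | 1 + 1.6 × 16.5/7.5 = 4.52 | 33.9/24 = 1.413 |
| 1.4, 8.5 | 1 + 1.4 × 15.5/8.5 = 3.55 | 30.2/24 = 1.258 |

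In the second and third rows totals PAL moves against activity. In the last two it moves with activity.

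**Non-wear (r = 1.5, s = 8; a full week is 224 sleep-hour kcal units over 56 sleep hours).** Each affected day below still has 18 worn hours.
- One day with 6 waking hours off: 215/56 = 3.84 (rate: 215/162 = 1.327).
- One night with 6 sleep hours off: 218/50 = 4.36 (rate: 218/162 = 1.346).
- Every day, 4 waking and 2 sleep hours off: 24/6 = 4.00, unchanged (rate: 24/18 = 1.333).
- Every day, 6 waking hours off: 23/8 = 2.875 (rate: 23/18 = 1.278).

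**Power at 77 per arm.** I assume an SD of 30 minutes for the change in mean sleep, independent of activity change. It adds an SD of 0.5 × 24r/64 = 0.188 to 0.281 on totals.
- If 0.22 already contains this variation: 80%, no loss.
- If 0.1 and 0.22 are rate-scale values, totals use 0.3 and 0.66. The SD becomes √(0.66² + 0.188²) = 0.686 to √(0.66² + 0.281²) = 0.717, and power is 77% to 73%.
- Rate-based PAL with the same rate-scale values: SD at most 0.2202, power 80%.

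**The case against.** The endpoint is a change from baseline compared between randomised arms. A stable sleep or removal habit largely cancels within the patient. Changes that are equal across arms add only noise. The reversals in the table describe single patients in chosen combinations, and the opposite pairings move the right way. Continuous wear is required, compliance is checked at the Week 1 and Week 6 calls, and proportional non-wear does nothing to the ratio. Every size above rests on assumed sleep hours, rates and SD. Steps, intensity durations and energy expenditure are analysed without division by SEE. All of this stands, and it limits the claim to sensitivity and interpretation.

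Three stronger readings are tempting, and the documents support none of them.
- **The comparison between arms is biased.** This needs sleep or wear to change differently by arm. An unblinded design allows that, but nothing in the documents shows it.
- **Power collapses.** If 0.22 were a totals-scale SD that excluded sleep variation, the 30-minute assumption would give an SD of √(0.22² + 0.188²) = 0.289 to √(0.22² + 0.281²) = 0.357, and power of 57% to 41%. No passage says that 0.22 was built that way.
- **The SAP contradicts the protocol, so the formula must be replaced.** Protocol 9.4.1 is ambiguous on the averaging unit, and Protocol 14.1 agrees with the SAP. SAP version 1.0 is dated 18 August 2020, after the April 2020 closure of an unblinded trial. Changing the primary derivation then would be hard to defend, and the rate version is not free of wear effects either.

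**Conclusion.** The point holds as one of interpretation. By the SAP's own definitions PAL responds to sleep length and to disproportionate non-wear as well as to activity. No safeguard in the plan removes this, since the 18-hour rule neither reaches the primary analysis nor requires worn sleep. The direction follows from the formula and needs no assumption beyond positive kcal rates. The size does need assumptions: with 8 h of sleep and a rate ratio of 1.0 to 1.5, about 10 to 17 minutes of sleep is worth 0.1, or about 30 to 53 minutes if 0.1 is a rate-scale value. Power loss runs from none to a fall to 73–77%, depending on the undocumented scale of 0.1 and 0.22 and on an assumed 30-minute SD. Bias between arms is possible but not shown.

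**What to change.** Keep the stated PAL as primary and make these additions:

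1. In SAP 6 and 11.5, add a named sensitivity analysis with both terms on the same time base: (wear-filtered kcal / worn minutes) / (sleep- and wear-filtered kcal / worn sleep minutes). Specify it without sight of treatment arm.
2. Report sleep hours, worn sleep hours and worn waking hours by arm for weeks 1 and 12. SAP 11.4 names device compliance but not these.
3. State that a PAL difference will not be attributed to activity alone unless the rate version agrees.
4. State the source and scale of 0.1 and 0.22, and reconcile the averaging unit in Protocol 9.4.1 with the SAP.

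The cost is a little more analysis work on ActiGraph data already held, and no patient leaves the primary analysis. The two versions may disagree, and that would have to be reported. The rate version still moves slightly with uneven wear (1.333 to 1.278 with 6 waking hours unworn every day at a ratio of 1.5), so it supports the primary result and is not a perfect measure of activity.

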10.1.3 Physical Activity Level

As it relates to the primary effectiveness endpoint, physical activity level (PAL) is the ratio of TEE to SEE, both as defined above, expressed as the following fraction:

Total Energy Expenditure (TEE)
Sleep Energy Expenditure (SEE)

10.1.4 Duration of Physical Activity

The duration of physical activity is the total number of wake- and wear-filtered minutes of physical activity performed in a day.

10.1.5 Intensity of Physical Activity

The intensity of the physical activity being performed is the categorization of the total X-, Y-, and Z-axis counts (vector magnitude unit or VMU) and the Y-axis count alone in a minute as one of the following:

- (SVLPA) Sedentary to Very Low: VMU < 3000
- (LMPA) Low to Moderate: VMU ≥ 3000 and Y-axis count < 1952
- (MVPA) Moderate to Vigorous: Y-axis count ≥ 1952

10.1.6 Steps Taken

The steps taken is the number of wear-filtered steps taken in a day.

10.2 Hospital Anxiety and Depression Scale

The Hospital Anxiety and Depression Scale (HADS) is a commonly used, validated questionnaire that measures anxiety and depression (Stern, 2014). The HADS consists of 14 questions about how the subject has been feeling over a preceding period, three months for the purposes of this study, with 7 pertaining to anxiety and 7 to depression.

Each question has four possible answers corresponding to a score between 0 and 3 that are added together to get a total score. The total scores for anxiety and depression are determined separately and are classified as one of the following:

- 0-7: Normal
- 8-10: Borderline abnormal (borderline case)
- 11-21: Abnormal (case)

10.3 Six Minute Walk Test

The Six-Minute Walk Test (6MWT), used in both practice and clinical research, assesses aerobic capacity and endurance. The 6MWT measures the distance (in meters) that can be walked on a flat, hard surface in six minutes.

10.4 St. George's Respiratory Questionnaire

The St. George's Respiratory Questionnaire (SGRQ) is a validated tool that can be used to measure health impairment in COPD patients. (Morishita-Katsu, et al., 2016). The SGRQ is a two-part questionnaire; Part 1 (questions 1-8) covers the patient's recollection of their symptoms over a preceding period, three months for the purposes of this study, and Part 2 (questions 9-16) addresses the patient's current state. The two parts are further categorized into three components: Symptoms (questions 1-8), Activity (questions 11 and 15), and Impacts (questions 9-10, 12-14, and 16-17).

Each possible answer for a question corresponds to a weight, between 0 and 100. The final score overall and for each component is the percentage of the total weight for selected answers out of the largest possible total weight for answers to the applicable questions. Higher final scores indicate more limitations.

11 General Statistical Considerations

11.1 Analysis Sets

11.1.1 Intention-to-Treat

The intention-to-treat analysis set (ITT) consists of randomized subjects who begin long-term oxygen therapy, with or without a POC, receive an ActiGraph device, and have at least baseline ActiGraph data. The ITT analysis set will be used as the primary analysis set in analyzing all endpoints.

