10.3 Visit 1: Randomization and Baseline Visit

After a potential study patient has 1) completed the initial informed consent process and signed the study-specific informed consent form, 2) successfully completed the baseline 6MWT, and 3) been determined to meet all inclusion criteria and none of the exclusion criteria, the patient will be randomized in a 1:1 ratio to either SOC long-term oxygen therapy only (control arm) or SOC long-term oxygen therapy plus a POC (treatment arm). Randomization will be stratified by site and will be implemented via small permuted blocks. Randomization assignments will be assigned through the electronic study database and will be obtained by trained site personnel. A patient is considered enrolled at the time of randomization. Patients will be given all study devices relevant to their study arm assignment and will receive training on all devices at the baseline visit. Patients will be instructed to contact their site study staff with any questions pertaining to the study.

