10.5.2 Data Management for the ActiGraph GT9X Device

A trained member of the study team will plug the device into the designated computer at the 12-week visit by following the instructions in the ActiGraph GT9X Link + CentrePoint Quick Start Guide and/or the ActiGraph Site User Guide (in the eTMF). The data will be automatically uploaded to the CentrePoint platform.

Additional data download instructions may be provided during study initiation and/or throughout the study as necessary. After data have been uploaded from the ActiGraph device, a trained study team member who uploaded the data should submit the data for data management and analysis as instructed in study training materials.

11 Concomitant Medications

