14.4 Other Statistical Considerations

Analysis Data Sets

At a minimum, two distinct analysis sets will be used for the evaluation of primary and secondary effectiveness endpoints. The *intent-to-treat analysis* set will include all randomized patients enrolled in the study. The *per protocol analysis* set will only include patients with complete primary effectiveness endpoint data and no major protocol violations. The safety evaluation will be based on the intent-to-treat analysis set only.

Justification of Pooling Data across Centers

A formal analysis will be conducted to determine the appropriateness of pooling data across the study centers. This will include constructing a linear regression model for the primary effectiveness endpoint with three factors: center, treatment and center by treatment interaction. Furthermore, “super-centers” may be constructed from centers with small numbers of enrolled patients to be entered into models as fixed effects.

Verification of Randomization Procedure

In order to verify the success of the randomization procedure, the distribution of each baseline and demographic variable of interest will be summarized by treatment group. Continuous variables will be summarized via mean, median, standard deviation, and range. Categorical variables will be summarized via counts and frequency distributions.

Missing Data

A sensitivity analysis will be performed for each endpoint to assess the potential impact of missing data on the results. A detailed description of all planned sensitivity analyses can be found in the Statistical Analysis Plan together with the analysis of the relevant endpoints. Missing values will be ignored for the summaries of baseline characteristics, other summaries and safety endpoints.

Standard Statistical Methods

Unless otherwise stated, all *P*-values will be considered significant at a two-sided significance level of 0.05. Summary statistics will be generated for all relevant variables. In the comparison of continuous variables, distributions will be tested for the normality assumption. If standard parametric techniques are found to be inadequate, an appropriate non-parametric technique or a Box-Cox transformation will be used. No corrections will be made for multiple testing procedures. All analyses will be conducted using SAS® version 9.1 or higher.

15 Risk Analysis

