16.4 Device Distribution to/from Patients

Upon being randomized to a study arm, all patients will receive an activity monitor and a diary to record oxygen usage. Patients who are randomized to the treatment arm will also receive the POC device assigned for distribution by his/her specific study site. At the time of device distribution, patients will be informed that they must return all study devices at the end of study participation. Patients are required to return all study devices (POC [if applicable], ActiGraph) to the site at the 12-week visit (or at study termination, if earlier). Sites will return the study devices to Sherpa Clinical Packaging in a bulk shipment at the end of the study. Patients will have the option to purchase their POC device used in the study.

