3.2.3 ActiGraph GT9X Link

All subjects enrolled in the study will receive an ActiGraph GT9X Link wearable device to collect physical activity data throughout the study. A CentrePoint (CP) data hub is also included with the ActiGraph device to upload the physical activity data.

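### SAP 11.1.1 calls its main analysis set ITT but requires baseline ActiGraph data, so the SAP plans no all-randomised comparison of exacerbation, respiratory hospitalisation or death, contrary to Protocol 14.4

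*SAP*

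**What the plan says.** Protocol 14.4 states that the intent-to-treat "set will include all randomized patients enrolled in the study". It applies its analysis sets to the primary and secondary effectiveness endpoints and adds: "The safety evaluation will be based on the intent-to-treat analysis set only". It names no set for exploratory endpoints.

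SAP 11.1.1 keeps the name but admits only "randomized subjects who begin long-term oxygen therapy, with or without a POC, receive an ActiGraph device, and have at least baseline ActiGraph data". It continues: "The ITT analysis set will be used as the primary analysis set in analyzing all endpoints". The only other set, per protocol (SAP 11.1.2), is drawn from within this one and serves only a sensitivity analysis of the primary endpoint. The missing-data analysis in SAP 11.5 covers week-12 PAL alone.

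On timing, Protocol 10.3 says: "A patient is considered enrolled at the time of randomization". Protocol 16.4 says: "Upon being randomized to a study arm, all patients will receive an activity monitor". SAP sections 6 and 7 take baseline activity values from the first study week. The trial is unblinded (Protocol section 3).

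**The concern.** Both documents use the name ITT, but for different populations, and the SAP neither mentions nor explains the change. The added data condition is met or failed after the patient and the site know the assignment. Someone who dies, is admitted or withdraws before giving usable wear data could therefore drop out of the mortality and hospitalisation comparisons, and the result would still be reported as ITT.

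A second route is a monitor that is never read. The scheduled download is at the end: "A trained member of the study team will plug the device into the designated computer at the 12-week visit". Protocol 12.2 lists death among the withdrawal reasons and relies on the patient to bring the devices back.

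If such losses differed between arms, they could bias the comparisons of exacerbation, respiratory hospitalisation and death. These endpoints do not depend on the monitor at all.

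**Working it through.** **1. Denominator.** SAP section 2 gives 109 enrolled of 190 planned: 109/190 = 57.4%, matching the stated 57%. Enrolment is randomisation (Protocol 10.3), so all-randomised means 109. Arms of 55 and 54 are assumed from the 1:1 ratio.

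**2. Which condition matters.** SAP 3.2.1 gives every enrolled subject standard oxygen, and Protocol 16.4 gives every randomised patient a monitor. Those two conditions should exclude almost nobody. The baseline-data condition is the one that may.

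**3. Endpoints against sets.**

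| Endpoint | Needs ActiGraph? | Set in Protocol 14.4 | Set in SAP 11.1.1 |
|---|---|---|---|
| Primary (PAL) | Yes | All randomised | Baseline ActiGraph required |
| Secondary 1 (diary oxygen use) | No | All randomised | Baseline ActiGraph required |
| Secondary 2, 3 (SGRQ, HADS, 6MWT) | No | All randomised | Baseline ActiGraph required |
| Secondary 4, 5 (exacerbation, respiratory hospitalisation; tested as means, SAP 7.1.1) | No | All randomised | Baseline ActiGraph required |
| Secondary 6 (steps) | Yes | All randomised | Baseline ActiGraph required |
| Secondary 7, 8 (mortality; tested as proportions, SAP 7.1.2) | No | All randomised | Baseline ActiGraph required |
| Exploratory 1–3 (hospitalisation) | No | None named | Baseline ActiGraph required |
| Exploratory 4–5 (activity, energy) | Yes | None named | Baseline ActiGraph required |

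For PAL the condition changes nothing, because SAP section 6 already requires both a baseline and a week-12 value.

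**4. How many could be excluded.** The documents do not say. For an assumed share of 0%, 2%, 5%, 10% or 15% of 109, the set would hold 109, 107, 104, 98 or 93.

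**5. Effect of one exclusion on an arm's proportion**, with n = 54 to 55 and k = 1 to 10 events (assumed):
- Patient with an event: k/n − (k−1)/(n−1). The largest fall is 1/54 − 0/53 = 1.85 points; the smallest is 10/55 − 9/54 = 1.52 points.
- Patient without an event: k/(n−1) − k/n. The largest rise is 10/53 − 10/54 = 0.35 points; the smallest is 1/54 − 1/55 = 0.03 points.

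**6. Assumed example, both directions** (treatment v control, Fisher exact):
- All randomised: 2/55 v 6/54, difference 7.47 points, p = 0.161.
- One control event lost: 2/55 v 5/53, difference 5.80 points, p = 0.266.
- One treatment event lost: 1/54 v 6/54, difference 9.26 points, p = 0.113.

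The conclusion at 0.05 is the same in all three. Tested as means, with one event per patient, the same losses move the control mean from 0.111 to 0.094, or the treatment mean from 0.036 to 0.019.

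**7. Lower end.** SAP 11.1.1 sets no minimum wear. Suppose any wear qualifies, every monitor is read, and only day-1 events are lost. With an assumed 12-week risk of 5% to 10% at a constant rate over 84 days, the events at stake are 109 × 0.05/84 = 0.065 to 109 × 0.10/84 = 0.130.

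**The case against.** The strongest reply is that the condition may exclude nobody. Withdrawn patients are to attend a final in-person visit and return their devices (Protocol 12.2). The week-1 call checks ActiGraph use (Protocol 10.4). A "data hub is also included with the ActiGraph device to upload the physical activity data", so data may reach the database before Visit 2. With no minimum wear, step 7 leaves well under one event at stake. The upper end of step 5 is also generous for deaths: 10/54 is 18.5% in 12 weeks, in a trial that excludes life expectancy under one year. The documents give no power calculation for any of these endpoints. All of this stands, and it limits what can be claimed about size. It does not remove the conflict. Calling the set primary leaves room for another, but the SAP defines no wider one.

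Three stronger readings are tempting but not supported:

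- **Safety.** A reader might infer that adverse events are also restricted, because SAP 5.4 lists them under Endpoints. SAP section 9, however, covers all adverse events during the study and names no analysis set. This is an ambiguity, not a shown conflict with Protocol 14.4.
- **Exploratory endpoints.** A reader might infer that the Cox model breaches the Protocol. Protocol 14.4 assigns no set to exploratory endpoints, so an all-randomised set there is a recommendation only.
- **Timing.** SAP version 1.0 is dated 18 August 2020, after closure on 30 April 2020. A reader might infer that the set was narrowed in the light of results. The documents do not show that anyone had seen results.

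**Conclusion.** Wrong as written, and it should be fixed. The SAP applies a post-randomisation data condition, under the name ITT, to endpoints that do not use the data. It departs from Protocol 14.4 and leaves secondary endpoints 4, 5, 7 and 8 with no all-randomised comparison. Secondary endpoints 1, 2 and 3 are restricted without need.

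Confidence is high for the textual conflict and low for any material bias. A reader might infer that the event results are biased, perhaps in favour of one arm. The documents show neither an exclusion nor a direction, and the number excluded may be zero. The shift of about 1.5 to 1.9 points per excluded patient with an event rests on assumed arm sizes and event counts, and the assumed example changes no conclusion at 0.05. The primary PAL result is not affected.

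**What to change.** 1. Define ITT as all randomised patients, analysed as randomised, and use it for secondary endpoints 4, 5, 7 and 8, in agreement with Protocol 14.4. For secondary endpoints 1, 2 and 3, use all randomised patients with available values and label this an available-case analysis.
2. As a recommendation, use the same all-randomised set for exploratory endpoints 1 to 3, with 2 and 3 remaining descriptive. The clock in the Cox model starts at enrolment, which is randomisation, so the population should be fixed at that point too.
3. Rename the present set modified ITT (ActiGraph-evaluable). Limit it to the primary endpoint, secondary endpoint 6 and exploratory endpoints 4 and 5. Tabulate exclusions by arm with reasons.
4. Add one sentence to SAP section 9 stating that adverse-event percentages use the all-randomised denominator.

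The cost is SAP wording and a few tables, with no new data collection. The small downside is that some early withdrawals will have unknown 12-week outcomes, because Protocol 12.2 leaves final-visit activities beyond device return to discretion. The medical-record review in Protocol 13.2.1 (Adverse Event Assessment) can recover part of this. The number still unknown should be reported by arm.
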